Oxymetazoline monotherapy, pilocarpine monotherapy, and concurrent dosing of pilocarpine and oxymetazoline in one or both eyes were found to be safe and well tolerated. No meaningful difference was seen between groups in the discontinuation rate or the incidence or severity of adverse events, with the exception of "eyelid retraction" which occurred most frequently in the oxymetazoline monotherapy group. No meaningful differences were seen between groups in visual analog scale (VAS) scores for temporal or supraorbital headache. It may require a larger sample size to detect ocular adverse events associated with pilocarpine monotherapy and to properly test AltaVista's finding of improved tolerability with the combination of oxymetazoline and pilocarpine relative to pilocarpine monotherapy.

The overall objective of this program is to develop a fixed-dose combination of pilocarpine and oxymetazoline for the treatment of presbyopia. To date, preclinical studies in rabbits and non-human primates, 4 pilot clinical studies conducted by AltaVista Instituto del Investigation Medica at the clinic of [name] [name], and Allergan study 199201-007 support the combination of pilocarpine and oxymetazoline for the treatment for presbyopia. These studies are summarized in the sections below.

1.4 Rationale for Study Design

Allergan Study 199201-007 achieved proof-of-concept for the current approach of treating presbyopia with a combination of oxymetazoline and pilocarpine ophthalmic solutions. This phase 2 clinical study is a systematic dose-response study designed to identify the optimum concentrations of oxymetazoline HCl (0.0125%, 0.05%, or 0.125%) and pilocarpine HCl (0.5%, 1%, or 1.5%) ophthalmic solutions dosed in combination for the improvement of UNVA in patients with presbyopia.

The results from Study 199201-007 suggest that pilocarpine improves UNVA in patients with presbyopia by decreasing pupil diameter which increases depth of focus. Oxymetazoline may further modulate the miotic effect of pilocarpine on UNVA by increasing both accommodation and duration. Study 199201-009 was designed to have more sensitivity to change in oxymetazoline concentration (ie, within patient comparison) than pilocarpine concentration (ie, between patient comparison). Secondarily, the current study brackets the concentration of pilocarpine used in 199201-007, the higher concentration of pilocarpine in the current study may result in a greater discontinuation rate. Thus, pilocarpine was selected as a between-patient variable to minimize any potential impact of patient discontinuation.

This study was designed to dose in the nondominant eye of younger presbyopic patients based on the results of 199201-007, as the greatest improvements in UNVA were seen with these two conditions. Due to the large number of comparisons when crossing over two drugs

each with 3 concentrations as well as monotherapies, it is not practical to use fixed combinations for all dose combinations in the current study. A fixed combination of pilocarpine 1% and oxymetazoline 0.125% was selected as the only fixed combination to enable bridging between the fixed combination used in this study and the unfixed combination used in this study and 199201-007.

Rationale for Dose Range

Oxymetazoline HCl has been marketed as an OTC medication for more than 3 decades in an intranasal spray containing 0.05% oxymetazoline HCl (under the brand name Afrin), and for over 2 decades in an eye drop solution containing 0.025% oxymetazoline HCl (under the brand names Visine LR and Ocuclear). Oxymetazoline systemic exposure has been measured after a single administration of Afrin nasal spray (3 sprays [0.1 mL/spray] in each nostril of 0.05% oxymetazoline, equating to 0.3 mg/dose), which resulted in a mean plasma maximal concentration (C_{max}) of 0.245 ng/mL and area under the curve from time 0 to 12 hours (AUC₀₋₁₂) of 1.74 ng·hr/mL (No serious adverse events were reported in this study and no patients discontinued prematurely due to an adverse event. There were no notable changes from predose to postdose in clinical laboratory tests, vital signs, electrocardiograms (ECGs), or IOP during the study.

The 0.125% dose of oxymetazoline used in Study 199201-007 resulted in a lower dose by weight (approximately 0.1 mg/dose) when compared to Afrin (0.3 mg/dose), based on the smaller ophthalmic dosing volume ($35~\mu L$). Results from Study 199201-007 showed that oxymetazoline monotherapy, pilocarpine monotherapy, and concurrent dosing of pilocarpine and oxymetazoline in one or both eyes were all safe and well tolerated. No meaningful differences were found between groups in discontinuation rate or in the incidence or severity of adverse events, with the exception of "eyelid retraction" which occurred most frequently in the oxymetazoline monotherapy group. No meaningful differences were found among groups in VAS scores for temporal or supraorbital headache. It may require a larger sample size and/or higher dose strengths of pilocarpine to detect ocular adverse events associated with pilocarpine monotherapy and to properly test AltaVista's finding of improved tolerability with the combination of oxymetazoline and pilocarpine relative to pilocarpine monotherapy.

In the AltaVista studies, no systemic or ocular adverse events were observed in 15 patients who were exposed to up to 3 drops of ophthalmic oxymetazoline within a 15-minute time period at concentrations up to 0.125%. Additionally, a nonclinical toxicology study demonstrated the safety of ophthalmic oxymetazoline at concentrations up to 0.25% when

administered BID for 28 days in combination with pilocarpine 1.0%. A nonclinical pharmacokinetic study evaluating the unfixed vs. fixed combination formulations demonstrated that pilocarpine absorption into the iris-ciliary body was slightly lower following administration of the fixed combination. This reduction in exposure was primarily driven by lower tissue concentrations at latter timepoints in the timecourse, potentially affecting clinical duration of action. Therefore, to achieve similar pilocarpine exposure in the target tissue, this study will evaluate a maximum pilocarpine dose of 1.5%.

Results from Study 199201-007 demonstrated that the combination of pilocarpine and oxymetazoline in the nondominant eye increased the peak effect and increased the duration of effect on UNVA in comparison to pilocarpine alone in the nondominant eye. The combination of pilocarpine and oxymetazoline dosed only in the nondominant eye demonstrated greater improvements in uncorrected near vision than oxymetazoline or pilocarpine alone dosed in only one eye or the combination dosed bilaterally. For both QD and BID dosing regimens, concurrent dosing of pilocarpine and oxymetazoline in either the nondominant eye (Group 3) or bilaterally (Group 4) showed consistent improvement over both oxymetazoline monotherapy (Group 1) and pilocarpine monotherapy (Group 2) in the percentage of patients achieving at least a 2 or 3 line improvement in mesopic, high-contrast, binocular UNVA at a majority of timepoints postdose. The effect of pilocarpine alone was found to mostly return to a baseline level 6 hours after administration, while the combination showed a continued effect 6 to 8 hours after administration. Oxymetazoline monotherapy was found to have little effect on UNVA. Thus, Study 199201-007 replicated the findings reported by AltaVista.

2. Study Objectives and Clinical Hypotheses

2.1 Study Objectives

To identify the optimum concentrations of AGN-199201 (and AGN-190584 when dosed in combination once a day for the improvement of UNVA in patients with presbyopia

2.2 Clinical Hypotheses

[figure not shown]
At least one concurrently dosed combination of AGN-199201 and AGN-190584 will:

- demonstrate a significant improvement in UNVA over monotherapy with AGN-199201 and monotherapy with AGN-190584 when they are dosed at the same concentrations as the combination
- 2. produce safety and tolerability findings no worse than cumulative findings with AGN-199201 monotherapy and AGN-190584 monotherapy when they are dosed at the same concentrations as the combination

3. Study Design

This study is a phase 2, multicenter, double-masked, parallel-group, randomized sequence, dose response, vehicle-controlled study in patients with presbyopia. Four groups (see Table 1) of different concentrations of AGN-190584 will be used to compare unfixed combinations with AGN-199201 and a fixed combination of AGN-190584 and a fixed combination of AGN-190584 and AGN-199201 solutions dosed in the nondominant eye during 5 dosing periods. For all 4 treatment groups, each dosing period will be once daily for 2 consecutive days, followed by a 7 to 21 day washout before the next 2-day dosing period, until exit after the fifth 2-day dosing period. The study duration will be 39 to 112 days per patient.

Following a screening visit (days -18 to -1) patients will be randomized at a baseline visit (visit 1) in a 1:1:1:1 ratio (stratified by the UNVA at baseline of $\leq 20/80$ and > 20/80) to 1 of the following treatment groups (also summarized in Table 1):

All patients will receive the fixed combination of AGN-199201 and AGN-190584 ophthalmic solutions within one of the 5 dosing periods. Vehicles for AGN-190584, AGN-199201, and the fixed combination ophthalmic solutions all have the same formulation.

Study medication will be administered once daily in each eye during office visits at hour 0 (8 AM \pm 1 hour) for 2 consecutive days during each dosing period. Dosing periods will be separated by a washout period of 14 ± 7 days. Eyes receiving both AGN-199201 and AGN-190584 are to receive a single drop of AGN-199201, followed approximately 5 to 7 minutes later by a single drop of AGN-190584. Eyes receiving the fixed combination of AGN-190584 and AGN-199201 are to receive a single drop of the fixed combination drug, followed approximately 5 to 7 minutes later by a single drop of vehicle. Eyes receiving vehicle alone are to receive 2 drops of vehicle, separated by approximately 5 to 7 minutes. The study design is depicted in Figure 1.

4. Study Population and Entry Criteria

4.1 Number of Patients

Approximately 160 patients (40 per group) will be enrolled at approximately 15 US sites. Approximately 35 patients per group are expected to complete the study based on an anticipated dropout rate of 12.5% (5 dropped patients per group).

[figure not shown]
4.2 Study Population Characteristics

[figure not shown]
The study population consists of adult patients who have objective and subjective evidence of presbyopia.

4.3 Inclusion Criteria

The following are requirements for entry into the study:

1. Male or female, ≥ 40 and ≤ 51 years of age

4.4 Exclusion Criteria

The following are criteria for exclusion from the study:

Ophthalmic:

1. Concurrent use of any topical ophthalmic medications, including artificial tears, other than the study medications, during the course of the study

[figure not shown]

- 4. Corneal abnormalities (including keratoconus, corneal scar, Fuchs' endothelial dystrophy, guttata, or edema) in either eye which are likely to interfere with visual acuity
- 5. History of cataract surgery, phakic intraocular lens (PIOL surgery), corneal inlay surgery, or any intraocular surgery.

10. Diagnosis of any type of glaucoma or ocular hypertension

4.5 Permissible and Prohibited Medications/Treatments

4.5.1 Permissible Medications/Treatments

The concurrent use of non-ocular medications that do not have a substantial effect on the pupil, accommodative properties, or retinal function of the eye is permitted during the study if a stable dosing regimen is established. The dosing regimen is not considered to be stable if a patient starts, stops, or changes the dose/drug during the study.

4.5.1.1 Definition of Females of (Non-)Childbearing Potential and/or Acceptable Contraceptive Methods

For purposes of this study, females will be considered of childbearing potential unless they are naturally postmenopausal (see definition below) or permanently sterilized (ie, hysterectomy).

Natural menopause is defined as the permanent cessation of menstrual periods, determined retrospectively after a woman has experienced 12 months of amenorrhea without any other obvious pathological or physiological cause. For women of childbearing potential who may participate in the study, the following methods of contraception, if properly used, are generally considered reliable: oral contraceptives, patch contraceptives, injection contraceptives, male condom with intravaginal spermicide, diaphragm or cervical cap with spermicide, vaginal contraceptive ring, intrauterine device, surgical sterilization (bilateral tubal ligation), vasectomized partner, or sexual abstinence.

The investigator and each patient will determine the appropriate method of contraception for the patient during their participation in the study.

4.5.2 Prohibited Medications/Treatments

Use of ocular medication(s) other than study medications administered to conduct study procedures (see Sections 6.3 and 6.4) are prohibited from the screening visit until study exit.

[figure not shown]
Use of medications that may have a substantial effect on visual function or the optical properties of the eye is prohibited from 2 weeks prior to the baseline visit and during the study:

- systemic medications with potential ocular side effects including topiramate, hydroxychloroquine, ethambutol, phosphodiesterase 5 (PDE5) inhibitors (sildenafil, vardenafil, tadalafil), or tamoxifen
- ophthalmic, systemic, or intranasal anticholinergics and α-adrenergic receptor agonists with potential pupillary or accommodative effects, including oxymetazoline, pilocarpine, tetrahydrozoline, phenylephrine, naphazoline, cyclopentolate, atropine, beta-blockers, or antihistamines
- systemic maprotiline, tricyclic antidepressants or monoamine oxidase inhibitors (MAOIs)

The decision to administer a prohibited medication/treatment is done with the safety of the study participant as the primary consideration. When possible, Allergan should be notified before the prohibited medication/treatment is administered.

5. Study Treatments

5.1 Study Treatments and Formulations

5.3 Methods for Masking

Study medication will be administered to each randomized patient at each dosing period by qualified site personnel. The investigator, investigational staff, and patients will be fully masked to study drug and vehicle treatments. All study treatments will be provided in identical multidose bottles and cartons.

5.4 Treatment Allocation Ratio and Stratification

Patients will be randomized in a 1:1:1:1 ratio into 1 of 4 treatment groups:

All patients will receive the fixed combination of AGN-190584 ophthalmic solution and AGN-199201 ophthalmic solution within one of the 5 dosing periods. The order of the dosing sequence in each group is shown in Table 3.

Patients will be stratified by UNVA at baseline of $\leq 20/80$ and > 20/80. For determination of stratification group assignment for each patient, sites will be required to enter the UNVA at baseline into the interactive response system (IxRS), and the IxRS will assign the stratum.

[figure not shown]
5.5 Method for Assignment to Treatment Groups/Randomization

Prior to initiation of study treatment, each patient who provides informed consent will be assigned a patient number that will serve as the patient identification number on all study documents.

[figure not shown]
At the time of randomization on visit 1, eligible patients will be placed into 1 of 2 strata as described in Section 5.4, and they will be assigned to 1 of the 4 treatment groups, in a masked fashion based on the randomization scheme within the patient's stratum according to the order of enrollment. The IxRS will assign the next available randomization number for the appropriate stratum to the patient at the time the investigator requests randomization. The IxRS will report 2 medication kit numbers (one for nondominant eye and one for dominant eye) to use for each patient corresponding to the randomization number. The randomization scheme will be prepared by Allergan Biostatistics.

[figure not shown]
Study medication will be labeled with medication kit number, study number, and dominant or nondominant eye. Each medication kit (carton) will contain 2 multidose bottles of study treatment; 1 bottle will be labeled with an 'X' and 1 bottle will be labeled with a 'Y'. The study treatment in each bottle will be administered in sequence (a single drop from bottle X first, followed 5 to 7 minutes later by a single drop from bottle Y). The IxRS will provide the site with the specific medication kit number(s) for each randomized patient at the time of randomization (day 1 of the first dosing period) and on day 1 of each subsequent dosing period. Sites will assign study medication kits according to the IxRS instructions. Sites will receive the IxRS confirmation notifications for each transaction. All notifications are to be maintained with the study source documents.

5.6 Treatment Regimen and Dosing

Study medication or vehicle will be administered once daily in each eye during office visits by designated site personnel at hour 0 (8 AM \pm 1 hour) for 2 consecutive days during each dosing period. Dosing periods will be separated by a washout period of 14 ± 7 days.

5.7 Storage of Study Medications/Treatments

The study product must be stored in a secure area. Only assigned study personnel, authorized by the investigator, may have access to study product. Study product will be administered only to patients entered into the clinical study, at no cost to the patient, in accordance with the conditions specified in this protocol.

[figure not shown]
All study products must be stored upright, in a refrigerator and protected from freezing. All study products will be stored within the temperature storage range limits required to ensure study product stability during the study. Sites must report any temperature excursion to Allergan, and avoid administering the impacted study product, by isolating the product, until receiving further instructions from Allergan (see Study Procedure Manual for more information).

[figure not shown]
5.8 Treatment Administration

[figure not shown]
Study medication or vehicle will be administered to each randomized patient once daily in each eye during office visits at hour 0 (8 AM \pm 1 hour) for 2 consecutive days during each dosing period by site personnel not otherwise involved in measuring safety, tolerability, or efficacy parameters. See Sections 5.3 and 5.6 for more detail.

[figure not shown]
- 6. Response Measures and Summary of Data Collection Methods
- **6.1** Efficacy Measures
- **6.1.1** Primary Efficacy Measure

[figure not shown]
The primary efficacy measure is mesopic, high contrast UNVA.

[figure not shown]

[figure not shown]

6.5 Summary of Methods of Data Collection

This protocol will use eCRFs with remote data capture through a qualified third-party vendor. Data entered into the eCRF will correspond to, and be supported by, source documentation maintained at the sites. The investigator is responsible for ensuring that data are properly recorded on each patient's eCRF and related documents. Data will be entered on the eCRFs in a timely manner and on an ongoing basis. An IxRS will be used to assign patient identification numbers, randomize patients, and manage study medication inventory. Data will be transferred to Allergan on a periodic basis throughout the study.

7. Statistical Procedures

One database lock is planned at the completion of the study. A detailed analysis plan (AP) will be approved prior to database lock.

7.1 Analysis Populations

The modified intent-to-treat (mITT) population is defined as all randomized patients with a baseline and at least 1 post baseline assessment of mesopic, high contrast, UNVA and will be analyzed as randomized. The efficacy variables will be analyzed using the mITT population.

[figure not shown]
The per protocol (PP) population is defined as all randomized patients who have no significant protocol deviations that affect the primary efficacy variable and complete all study visits. The PP population will be determined prior to database lock. The primary efficacy variable will also be analyzed using the PP population on an as-treated basis.

The safety population is defined as all patients who received at least 1 dose of study treatment and will be analyzed as treated. All safety measures will be analyzed using the safety population.

7.2 Collection and Derivation of Primary and Other Efficacy Assessments

7.2.1 Primary Efficacy Variable

The primary efficacy variable is the weighted average change from baseline in UNVA letter in the nondominant eye over 2-day periods between hour 1 and hour 10. Baseline will be the hour 0 measure for each dosing period.

7.3 Hypothesis and Methods of Analysis

[figure not shown]
In general, continuous data will be summarized with descriptive statistics (number of patients, mean, standard deviation, median, minimum, and maximum) and will be analyzed using mixed model, analysis of variance (ANCOVA) techniques or 2-sample t-tests (for between-group comparisons) and paired t-tests (for within-group analyses). Categorical variables will be analyzed using Pearson's chi-square test, Fisher's exact test, or Cochran-Mantel-Haenszel (CMH) test.

[figure not shown]
There will be no adjustment of type I error rate for the multiple tests. A 2-sided test with a p-value ≤ 0.05 will be considered statistically significant.

There will be no imputation of missing data for the all analysis.

7.3.1 Primary Efficacy Analyses

For the primary efficacy analysis, the weighted average change from baseline will be analyzed using a mixed model with treatment group, dosing period, baseline UNVA, and iris color as fixed effects.

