
The per protocol (PP) population is defined as all randomized patients who have no significant protocol deviations that affect the primary efficacy variable and complete all study visits. The PP population will be determined prior to database lock. The primary efficacy variable will be analyzed using the PP population on an as-treated basis.

The safety population is defined as all patients who received at least 1 dose of study treatment and will be analyzed as treated. All safety measures will be analyzed using the safety population.

In general, continuous data will be summarized with descriptive statistics (number of patients, mean, standard deviation, median, minimum, and maximum) and will be analyzed using mixed model techniques or 2-sample t-tests (for between-group comparisons) and paired t-tests (for within-group analyses). Categorical variables will be summarized by sample size (N), frequency count and percent, and will be analyzed using Pearson's chi-square test, Fisher's exact test, or Cochran-Mantel-Haenszel (CMH) test.

There will be no imputation of missing data for all analysis.

Efficacy:

The primary efficacy variable is the weighted average change from baseline in UNVA letters in the nondominant eye over two-day dosing periods between hour 1 and hour 10. Baseline will be the hour 0 measure for each dosing period. For the primary efficacy analyses, the weighted average change from baseline will be analyzed by response surface approach using a mixed model with treatment group, dosing period, baseline UNVA, and iris color as fixed effects.

A UNVA responder is defined as a patient with at least a 3 line improvement in mesopic, high contrast, UNVA from baseline (hour 0 of visit 1) at most of the postdose time points in the nondominant eye. The proportion of the UNVA responders will be compared by frequency distribution.

There will be no adjustment for multiple tests.

Detailed descriptions will be documented in analysis plan.

Safety:

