### 4.1 Study Design Summary

This study is a phase 2b, multicenter, double-masked, parallel-group, randomized sequence, dose response, vehicle-controlled study in patients with presbyopia. Sixteen unfixed combination of AGN-190584 [REDACTED] and AGN-199201 ([REDACTED]) and a fixed combination of AGN-190584 [REDACTED] and AGN-199201 [REDACTED] solutions will be dosed in the nondominant eye during 5 dosing periods. For 17 different treatment combinations, each dosing period will be once daily for 2 consecutive days, followed by a 7 to 21 day washout before the next 2-day dosing period, until exit after the fifth 2-day dosing period. The study duration will be 39 to 112 days per patient.

Following a screening visit (days -18 to -1) patients will be randomized at a baseline visit (visit 1) in a 1:1:1:1 ratio (stratified by uncorrected near vision acuity at baseline of  $\leq 20/80$  and  $> 20/80$ ) to 1 of the following treatment groups:

- Group 1: AGN-199201 [REDACTED] and AGN-190584 vehicle 0%
- Group 2: AGN-199201 [REDACTED] and AGN-190584 ophthalmic solution [REDACTED]
- Group 3: AGN-199201 [REDACTED] and AGN-190584 ophthalmic solution [REDACTED]
- Group 4: AGN-199201 [REDACTED] and AGN-190584 ophthalmic solution [REDACTED]

All patients will receive the fixed combination of AGN-199201 [REDACTED] and AGN-190584 [REDACTED] ophthalmic solutions within one of the 5 dosing periods. Vehicle for AGN-190584, vehicle for AGN-199201, and the vehicle for fixed combination ophthalmic solution have the same formulation.

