### **5.1.1.1.3 Statistical Methodology**

The methodologies defined below apply as specified to individual endpoints defined in this SAP. When indicated, 95% two-sided confidence intervals and two-sided p-values will be presented.

Individual endpoint analyses may specify exceptions (additions or deletions) to these general definitions.

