**Table 5-3 Statistical Methodology**

Methodology		Description
M1	Categorical counts	
 
• Number of subjects in individual categories               
 
○ Subjects with <math>\geq 1</math> qualifying event counted once per individual category
 
 
 

M2	Categorical descriptives	
 
• Number and percentage of subjects in individual categories               
 
○ Subjects with <math>\geq 1</math> qualifying event counted once per individual category
 
 
 
• (Optional) N included if percentage denominator <math>\neq</math> number of subjects in the population (standard percentage denominator).
 

M3	PCS descriptives	
 
• Number and percentage of subjects meeting potentially clinically significant (PCS) criteria               
 
○ Subjects with <math>\geq 1</math> qualifying event counted once per PCS category
 
 
 
• Percentage denominator = number of subjects with non-missing baseline and <math>\geq 1</math> non-missing postbaseline assessment
 
• Unevaluable assessments considered missing
 

M4	Continuous descriptives	
 
• N included, mean, standard deviation (SD), median, minimum, maximum
 
• N included = subjects with non-missing value
 

M5	CFB descriptives	
 
• Continuous descriptives for baseline, postbaseline, and change from baseline (CFB) values
 
• N included = subjects with non-missing values at both baseline and the specified postbaseline analysis visit
 

M6	CFB ANCOVA	
 
• Continuous descriptives and standard error (SE) for baseline, postbaseline, and CFB values
 
• Estimates derived from mixed model for CFB value controlling for factors (pilocarpine dose, oxymetazoline dose) and covariates (baseline UNVA severity, iris color)               
 
○ Least squares (LS) means and standard errors
 
○ P-values from contrast t-test comparing active AGN-199201 treatment groups vs AGN-199201 vehicle
 
 
 
• N included = subjects with non-missing values at both baseline and the postbaseline analysis visit
 

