M7	CFB MMRM	
 
• Continuous descriptives and SE for baseline, postbaseline, and CFB values at each analysis visit               
 
○ N included = subjects with non-missing values at both baseline and the postbaseline analysis visit
 
 
 
• Estimates derived from mixed model for CFB value controlling for fixed factors (pilocarpine dose, oxymetazoline dose,), covariates (baseline UNVA severity, iris color), and interactions (pilocarpine dose and oxymetazoline dose interaction), with an compound symmetry covariance matrix               
 
○ LS means and standard errors
 
○ N included = subjects with non-missing values at both baseline and postbaseline analysis visit
 
 
 

M8	CFB figure	
 
• Plot of CFB LS means and SE bars for each treatment group.
 

M9	CFB RS figure	
 
• Plot of CFB response surface in 3 dimension.
 

M10	Responder	
 
• Categorical descriptives for responders and nonresponders               
 
○ Nonresponders include:                   
 
▪ Subjects who do not meet responder criteria
 
 
 
 
 

CFB = change from baseline; ANCOVA = analysis of covariance; ANOVA = analysis of variance.

MMRM = mixed model for repeated measures; RS=response surface

Raw and derived data listings will be provided, and will be fully defined in the table, figure, and data listing specification document.

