**Table 5-15 Mesopic, High Contrast UNVA Analyses**

Endpoint	Description	Timing	Methodology
Average change from baseline in UNVA letters (Primary efficacy variable)	Average change from baseline in UNVA letters  in the nondominant eye over two-day dosing periods between hour 1 and hour 10.	Treatment Period	CFB MMRM  CFB ANCOVA  CFB RS figure CFB figure
[REDACTED]	[REDACTED]	[REDACTED]	[REDACTED]
[REDACTED]	[REDACTED]	[REDACTED]	[REDACTED]
[REDACTED]	[REDACTED]	[REDACTED]	[REDACTED]
[REDACTED]	[REDACTED]	[REDACTED]	[REDACTED]
[REDACTED]	[REDACTED]	[REDACTED]	[REDACTED]

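### Dosing period is a fixed effect of the primary model in the protocol but is not listed in the SAP methods printed for the primary variable; restore it there, mainly to protect precision

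*Protocol*

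**What the plan says.** Protocol 7.3.1 states that the primary variable is to be "analyzed using a mixed model with treatment group, dosing period, baseline UNVA, and iris color as fixed effects". The Protocol Summary, under Efficacy, names the same four fixed effects and calls the analysis a response surface approach.

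SAP Table 5-15 assigns two model-based methods to the primary variable: CFB MMRM (marked with footnote 2) and CFB ANCOVA (footnote 3). Both are defined in SAP Table 5-3. M7 (CFB MMRM) is a mixed model "controlling for fixed factors (pilocarpine dose, oxymetazoline dose,), covariates (baseline UNVA severity, iris color), and interactions", the interaction being that of the two doses, with a compound symmetry covariance matrix. M6 (CFB ANCOVA) has the same two dose factors and the same two covariates, without the interaction. Neither list contains dosing period. The only p-values printed in M6 are described as "P-values from contrast t-test comparing active AGN-199201 treatment groups vs AGN-199201 vehicle".

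SAP 5.1.1.1.3 adds a general reservation: "Individual endpoint analyses may specify exceptions (additions or deletions) to these general definitions". The readable part of SAP 5.2.2 declares changes to the name of the variable, the responder analysis, the subgroups and the mITT definition. It says nothing about the fixed effects of the primary model.

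**The concern.** Each patient is treated in five dosing periods, so dosing period is a design factor. The SAP's two dose factors can stand in for the protocol's treatment group. Nothing printed stands in for dosing period: compound symmetry describes the correlation within a patient and does not absorb a shift in the mean from one period to the next.

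The stake is mainly precision. If the change from hour 0 differs by period, for example through practice within the test day, that variation stays in the residual. Standard errors of within-patient contrasts are then too large. Those contrasts are the oxymetazoline comparisons, to which Protocol 1.4 says the study was meant to be more sensitive, and they carry M6's only printed p-values.

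Bias is a lesser risk. It needs period effects together with dropout that differs between groups, and it would fall on the between-patient pilocarpine contrast. Protocol 1.4 says only that discontinuation may be greater at the higher pilocarpine concentration.

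**Working it through.** **The plan's own figures.** Protocol 7.5: 5 sequences × 8 = 40 patients per group, and 4 × 40 = 160. Protocol 4.1: 40 × (1 − 0.125) = 35 completers per group. SAP 5.1.2: 160 × (1 − 0.10) = 144 completers. All reproduce. There is no power figure to reproduce, because neither document states an SD, effect size or power.

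**Assumed inputs.** Within-patient SD of 3, 4 or 5 letters. Three patterns of period effect in the change from hour 0, in letters over periods 1 to 5. The sequence table is not readable, so I assume the five sequences are balanced over periods (a Latin square), which fits 5 sequences of 8 patients.

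**Precision.** With period omitted, the within-patient residual variance grows by about the sum of squared deviations of the period effects divided by 4:

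- (0, 1, 2, 3, 4): 10 / 4 = 2.5
- (0, 0.5, 1, 1.5, 2): 2.5 / 4 = 0.625
- (3, 0, 0, 0, 0): 7.2 / 4 = 1.8

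The ratio of the reported to the correct standard error is R = √(1 + added / SD²). On balanced data the estimate's true sampling variance does not change, so the actual two-sided level is 2 × (1 − Φ(1.96 R)). A contrast with 80% power when period is modelled has power Φ(2.80 − 1.96 R) without it.

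| Period pattern | SD | R | Actual level | Power |
|---|---|---|---|---|
| 1 letter per period | 5 | 1.049 | 0.040 | 77.2% |
| | 4 | 1.075 | 0.035 | 75.6% |
| | 3 | 1.130 | 0.027 | 72.1% |
| 0.5 letter per period | 5 | 1.012 | 0.047 | 79.3% |
| | 4 | 1.019 | 0.046 | 78.9% |
| | 3 | 1.034 | 0.043 | 78.1% |
| 3 letters extra in period 1 only | 5 | 1.035 | 0.042 | 78.0% |
| | 4 | 1.055 | 0.039 | 76.9% |
| | 3 | 1.095 | 0.032 | 74.4% |

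As a check, an exact least-squares calculation for one group of 40 with patient effects and a total drift of one residual SD (1 letter per period at SD 4) gave zero bias and an SE ratio of 1.077. By hand: 40 × 0.625 / 156 = 0.160, and √1.160 = 1.077.

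**Bias.** Simulated generalised least squares with compound symmetry and no period term: 4 groups × 5 cyclic sequences × 8 patients, dropouts leaving after period 1, 2, 3 or 4 with equal chance, 300 draws per setting, Monte Carlo SE at most 0.008. Assumed dropout is 5%, 5%, 12.5% and 25% in groups 1 to 4, with groups 2 to 4 taken as ascending pilocarpine concentration and a drift of 1 letter per period. Bias in group 4 minus group 2, in letters, by within-patient correlation ρ:

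| Coding of fixed-combination data | ρ = 0.4 | ρ = 0.6 | ρ = 0.8 |
|---|---|---|---|
| One common treatment (the 17 treatments of SAP 4.1) | −0.119 | −0.087 | −0.049 |
| As its dose pair | −0.122 | −0.086 | −0.064 |
| Separately by group | −0.193 | −0.218 | −0.235 |
| Excluded | −0.177 | −0.202 | −0.221 |

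With 17 treatments and 0.5 letter per period the values are −0.060, −0.045 and −0.022. With 3 letters extra in period 1 they are +0.085, +0.070 and +0.042. With 12.5% dropout in every group, all codings lie within 0.015 of zero. Within-group oxymetazoline contrasts have mean absolute bias below 0.015 in every coding.

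**Degrees of freedom.** With complete data and 17 treatments, 160 × 4 − 16 = 624 within-patient degrees of freedom, or 620 with a five-level period term.

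**The case against.** The strongest objection is that the deciding text cannot be seen. Footnotes 2 and 3 of Table 5-15 sit on exactly these two methods, SAP 5.1.1.1.3 lets an endpoint add terms, and several rows of the SAP amendment tables are redacted. SAP 5.1 also describes the SAP as expanding the protocol's statistical section, so silence in 5.2.2 could mean that the protocol model still stands. This holds as far as it goes: it cannot be said that the term was dropped. But the M6 and M7 lists are complete as printed and specific to this study (they name the two drugs and iris color), and they do not match the protocol sentence. If a footnote restores the term, Table 5-3 still needs to agree with it.

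Second, the period effect may be small. Baseline is reset at hour 0 of every period, which removes any drift shared by hour 0 and the postdose measures, and periods are separated by 7 to 21 days. A drift of 1 letter per period means 4 letters in the change score between periods 1 and 5, and nothing in the documents supports that size. At half that drift the loss is 1 to 2 points of power, and the error is on the conservative side. This stands and limits the weight of the point. Still, the protocol defines the per-period baseline and keeps dosing period in the model as well.

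Third, the bias figures need unequal dropout that the protocol does not plan for. That is correct, and bias is treated here as secondary.

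**Conclusion.** The printed model lists in SAP Table 5-3 disagree with Protocol 7.3.1 and the Protocol Summary on dosing period, and no readable text declares or explains the difference. If M6 and M7 are run as printed, the likely harm is lost precision in the within-patient oxymetazoline contrasts. It runs from slight (standard errors 1 to 3% too large at 0.5 letter per period) to moderate (5 to 13% at 1 letter per period). Bias in the pilocarpine contrast is about zero under the planned equal dropout and 0.05 to 0.12 letters under the assumed 25% versus 5% dropout with the fixed combination as one treatment.

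These sizes rest on assumed SDs, period effects and dropout, and on sequences balanced over periods. If that balance failed, bias would matter more: in an illustrative layout with one treatment always in period 5, a total drift of one residual SD gave a bias of 0.70 residual SD. Confidence is medium because the footnotes are not visible. The point should be settled before database lock but does not threaten the study.

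**What to change.** Add dosing period (5 levels) as a fixed effect to both M6 and M7 in SAP Table 5-3, leaving Protocol 7.3.1 as it is. If footnotes 2 and 3 of Table 5-15 already add the term, change Table 5-3 to agree with them. If the omission is intended, SAP 5.2.2 must declare and justify it; that would reconcile the documents but would not recover the precision, so adding the term is the better course.

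The cost is one line of SAP wording and 4 of about 620 within-patient degrees of freedom. The sample size does not change.
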